11.1.3. Primary Efficacy Analysis: Time to Complete Eschar Removal

The primary efficacy variable will be analyzed using the FAS. Missing data for the main primary analysis and for the three sensitivity analyses will be handled by the methods described in Section 10.1.2. In addition, the primary analysis will be repeated for the PP collective as sensitivity analysis.

Time until complete eschar removal will be defined as the time until complete eschar removal has been achieved for all TWs. This will be measured as time from the randomization date (days). Kaplan-Meier curves will be presented graphically to display the distribution of time to complete eschar removal under the two treatments. Median time to complete eschar removal

will be estimated for each treatment group with a 95% confidence interval. Furthermore, descriptive statistics for time to complete eschar removal will be presented. The treatment groups will be compared using a Cox regression model. The comparison will be adjusted for clinical center, age, %TBSA, proportion of the FT area of a patient and number of TWs (1,2,3-4, ≥5) by including each of them in the Cox regression model together with the treatment variable (NexoBrid vs. SoC). The treatment groups will be compared by testing the null hypothesis of no difference, comparing the ratio of the estimated treatment coefficient to its standard error to a standard normal distribution.

The Cox Regression analysis outlined above will be performed if the proportional hazards assumption appears to hold. This will be checked by including in the regression model a variable representing the interaction between time since randomization and treatment group. This coefficient will be tested (on actual sample allocation, without the re-randomization test) to be nonzero. Additionally, a log likelihood test comparing the model fit of a model with all time by covariate interactions added with a model without these interactions will be computed. The proportionality assumption will be rejected if one of these tests yields a significant result at the 10% level. In this case, we will use a generalized Wilcoxon-Gehan test. The Wilcoxon-Gehan test will be performed using the Wilcoxon option (also provided by default) in the SAS procedure PROC LIFETEST using the following SAS Code:

```
PROC LIFETEST DATA=burn_data;
TIME time*status(0);
STRATA agegroup ftgroup numtw tbsagroup centergroup / GROUP = treatment_group;
RUN;
```

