Here burn_data is the data set containing all necessary information. The variable time is the time to complete eschar removal, status is a censoring variable (0 for censor and 1 for complete ER event) and agegroup, ftgroup, numtw, tbsagroup, and centergroup are the variables, which the model is adjusted for. Agegroup, ftgroup, tbsagroup and centergroup are the stratification levels defined in Section 11.1.11 and numtw is the number of target wounds $(1, 2, 3-4, \ge 5)$.

Supportive analyses will include adjustment for other baseline variables that are imbalanced, based on the analyses described in Section 11.1.1.

The comparison between treatments will also be conducted on the time to complete eschar removal measured from the date of ICF as an additional analysis.

As an additional analysis, time to complete eschar removal will be analyzed on a target wound level using a method of survival analysis with clustered data that is based on appropriate assumptions. By "clustered data", we refer to the multiple target wounds that can occur in a patient. The proportional hazards assumption will be checked in the same way as in the patient level analysis. I.e. a Cox regression model will be fitted with covariates treatment, center, age, %TBSA, proportion of the FT area of a patient, number of TWs (1,2,3-4, ≥5) and a variable representing the interaction between time since randomization and treatment group. The latter coefficient will be tested to be nonzero. Additionally, a log likelihood test comparing the model fit of a model with all time by covariate interactions added with a model without these interactions will be computed. The proportionality assumption will be rejected if one of these tests yields a significant result at the 10% level. If the proportional hazards assumption is appropriate we will use a marginal Cox regression analysis with a robust sandwich estimator. If not, then we will use a parametric frailty model. Either method can be implemented in SAS (see Gharibvand and Liu, 2009 for details). The marginal Cox regression model is implemented in the PHREG procedure and the robust variance option is implemented by specifying the COVS(AGGREGATE) option. This induces the use of the robust variance method of Binder et. al. [22]. The parametric frailty model will be implemented using the following SAS-code:

```
PROC PHREG DATA=burn_data;

CLASS Subject_id treatment_group centergroup numtw;

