where subject_ID is a unique identification number for each patient, time is the time to wound closure on a wound level. Censor is a censoring indicator, treatment_group gives the treatment group, age1-age3 are indicator variables for a subject being in age group A1 − A3 respectively (per age groups defined in Section 11.1.11), ft1is an indicator for a subject with proportion of the FT area <20% out of the total burned area (group C1, defined in Section 11.1.11), TBSA1 is an indicator for a subject with overall %TBSA in (1% to 15%), inclusive (group B1, defined in Section 11.1.11), number_tw2 is an indicator variable for the subject having 2 target wounds (patient level), number_tw3 is an indicator variable for the subject having 3-4 target wounds (patient level), number_tw4 is an indicator variable for the subject having ≥5 target wounds (patient level), US, EEU and WEU are indicator variables for the individual being in region US, EEU and WEU (patient level) and burn_data is a SAS data set containing the required information.

Kaplan-Meier curves will be presented graphically to display the distribution of time to complete wound closure under the two treatments.

If any of the baseline factors are found to be significantly different between the treatment groups (based on the analyses described in Section 11.1.1), then the factor will be included as an extra adjusting covariate in a supportive analysis of time to complete wound closure.

As an additional analysis, the time to complete wound closure will be analyzed on a subject level. Kaplan-Meier curves will be presented graphically to display the distribution of time to complete eschar removal under the two treatments on a subject level. Median time to complete eschar removal will be estimated for each treatment group with a 95% confidence interval. Furthermore, descriptive statistics for time to complete eschar removal will be presented. The treatment groups will be compared using either a Cox regression model (if the proportional hazards assumption appears to hold), or a generalized Wilcoxon-Gehan test (if the proportional hazards assumption does not hold), as described in Section 11.1.3 for the main analysis of the primary efficacy endpoint.

As supportive analyses, the time to reach 100% wound closure will be analyzed on a wound level (similar to the main analysis outlined above) and on a subject level (similar to the additional analysis outlined above).

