11.1.8. Multicenter Data

Randomization will be stratified by center as detailed in the Section 15.7.2 of the protocol.

The analyses of the primary and secondary endpoints of this trial will adjust for possible center effects by including the grouped center as covariate in the analyses. The grouping will be done using the geographical regions: US (United States), EEU (Eastern Europe), WEU (Western Europe) and India.

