11.1.9. Handling of Multiple Comparisons

Unless otherwise specified, all statistical tests will be conducted against a two-sided alternative hypothesis, employing a significance level of 0.05. The primary and secondary endpoints of efficacy will be tested in a hierarchy, so as to preserve the nominal significance levels:

- 1. Primary: time to complete eschar removal
- 2. Secondary: Incidence of surgical excision
- 3. Secondary: Blood loss
- 4. Secondary: Area of Autograft in DPT wounds

5. Secondary: Incidence of Autograft in DPT wounds

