11.1.11. Stratification

The following factors are used to stratify the study design:

A. Age group:

A1: 0 to 23 month

A2: 24 months to 3 years

A3: 4 to 11 years

A4: 12 to 18 years

B. Overall total area of burns measured by % of TBSA

B1: (1% to 15%), inclusive

B2: (> 15% to \leq 30%)

C. The proportion of the FT area out of the total burned area of a patient

C1: < 20% of the burned area defined as FT

C2: ≥ 20% of the burned area defined as FT

D. Clinical center, so as to address possible differences in SoC procedures between sites (if any), to allow comparison of the results within center and to reduce the likelihood of a center including patients in only one arm of the study.

 $D_1, D_2,...,D_m$ (m being the number of participating clinical centers).

Using this stratification, patients will be randomized in a 1:1 ratio (NexoBrid: SoC).

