13.3. Update to Study Sample Size Due to COVID-19 Pandemic

According to the study protocol version 9.01 dated 29 July 2019, 160 patients were to be enrolled into the study according to the defined age group distribution. Prior to the outbreak of COVID-19 pandemic and until March 2020, 145 patients were enrolled into the study.

The COVID-19 pandemic significantly affected all study sites' ability to enroll additional patients. There was a great uncertainty regarding when restrictions would be lifted and study sites would be able to resume enrollment. Therefore, MediWound explored whether the recruitment to the study can be completed at this stage, with 145/160 (91%) of patients

enrolled, in line with FDA guidance document: "Statistical Considerations for Clinical Trials During the COVID-19 Public Health Emergency", issued on 17 June 2020.

The original sample size and statistical power calculations for this study were based on effects reached during the first Phase 3 study (MW2004-11-02) which was completed in 2009. Since then MediWound had also completed the recruitment and the 12 month follow up of 175 adult patients randomized to the Phase 3 study MW2010-03-02 (DETECT). Power calculations were performed also using data from this latest phase 3 study.

The updated sample size calculations, presented below, confirmed that based on a sample size of 145 patients, the study is sufficiently powered to meet the primary and main secondary and safety endpoints as originally planned. Thus, the study provides all required data to evaluate NexoBrid's safety and efficacy in pediatric patients while enabling the early availability of the product to address an unmet need in the pediatric population. These power calculations were submitted to the pediatric committee (PDCO) within the EMA and to the FDA to support MediWound's request for early completion of enrollment.

The request for early study completion was endorsed by the study's DSMB, relying on the confirmation that study endpoints can be met with the sample size of 145 patients and pending FDA and EMA approval.

The request for early completion of enrollment was accepted by both the FDA and the PDCO (EMA) and therefore the enrollment of patients into the study was completed with a total of 145 patients, with the following age distribution:

- 45 patients ≥0 months and ≤23 months old
- 30 patients ≥24 months and ≤3 years old
- 50 patients ≥4 years and ≤11 years old
- 20 patients ≥12 years and <18 years old

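### The fallback primary test crosses five factors into 256 possible strata for 145 patients, with no rule for one-arm strata; if it is triggered, power can be lost

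*SAP*

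**What the plan says.** SAP 11.1.3 compares the arms on time to complete eschar removal with a Cox model adjusted for center, age, %TBSA, FT proportion and number of target wounds (TWs), each entered as its own term. Proportional hazards is checked by a treatment-by-time interaction and by a likelihood test of all covariate-by-time terms. The rule is: "The proportionality assumption will be rejected if one of these tests yields a significant result at the 10% level". The main test then becomes a generalized Wilcoxon-Gehan test in PROC LIFETEST, with the statement "STRATA agegroup ftgroup numtw tbsagroup centergroup / GROUP = treatment_group".

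For the levels, 11.1.3 states: "Agegroup, ftgroup, tbsagroup and centergroup are the stratification levels defined in Section 11.1.11". Number of TWs has four categories (1, 2, 3–4, ≥5). Section 11.1.11 lists center as D1 to Dm, "m being the number of participating clinical centers". Section 11.1.8, however, adjusts the primary and secondary analyses for a grouped center: "The grouping will be done using the geographical regions", namely US, Eastern Europe, Western Europe and India. No section says what to do with strata that are sparse or hold one arm only.

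Section 13.3 gives two sizing scenarios for this endpoint at 90% power: 42 patients under the Cox model (from MW2004-11-02), and 94 patients under the Gehan test (from MW2010-03-02, where proportional hazards had been rejected). It does not state the strata used in the second.

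**The concern.** The Cox model spends a few coefficients on these factors. The fallback crosses them. Minimization (13.1) balances the margins of age, TBSA, FT and center but not their cross, and number of TWs is not a minimization factor. One-arm cells are therefore to be expected. Patients in such cells stay in the full analysis set and in the Kaplan-Meier curves but have no influence on the test.

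The fallback is a live branch, since one of the two sizing scenarios assumes it. Under 11.1.9, "The primary and secondary endpoints of efficacy will be tested in a hierarchy", with this endpoint first. Power lost here therefore also puts the four secondary endpoints at risk.

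**Working it through.** 1. **The plan's own figure.** D = 4(1.96 + 1.28)² / 1.25² = 26.9, and n = 2 × 26.9 / (0.59 + 0.70) = 41.7, against 42 stated. It reproduces. The N = 94 cannot be reproduced, because its data and strata are not given.

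2. **Cells.** Age 4 × FT 2 × TWs 4 × TBSA 2 × region 4 = 256 possible cells, or 145 / 256 = 0.57 patients per cell.

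3. **Why one-arm strata drop out.** At an event time with d events and n at risk, n₁ of them on NexoBrid, the stratum contributes observed minus expected = d₁ − d·n₁/n, with variance proportional to (n₁/n)(1 − n₁/n). If n₁ is 0 or n throughout, both are zero.

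4. **Share of patients affected.** The age split 45/30/50/20 is from 13.3. All else is assumed, with 145 patients allocated by minimization as in 13.1 and 32 centers:

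| Assumed split | FT ≥20% | TBSA >15% | TWs (1 / 2 / 3–4 / ≥5) | Regions | One-arm share |
|---|---|---|---|---|---|
| Spread | 40% | 30% | 40/25/25/10 | 25/30/25/20 | 65% |
| Moderate | 30% | 15% | 50/25/20/5 | 20/40/20/20 | 50–51% |
| Concentrated | 15% | 7% | 65/20/12/3 | 10/55/20/15 | 32–33% |

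The shares in the table are for independent factors. With correlated factors included, the range is 28–65%, with 52–100 cells occupied on average. Extreme splits give 17% (FT 5%, TBSA 5%, TWs 85/10/4/1, regions 5/85/5/5) and 73% (all even). Patients left in two-arm strata: 145 × 0.70 ≈ 101 down to 145 × 0.35 ≈ 51. With region alone the one-arm share is 0%, with region × age 1–3%, and with age × FT × TBSA 2–3%.

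5. **Fallback power at N = 145** (times in whole days, SoC median of 6 days assumed):

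| Effect | 256 cells | Coarse strata |
|---|---|---|
| SAP target, log HR 1.25 (HR 3.49), no censoring | 82–99% | 100% |
| Calibrated so that an unstratified Gehan test has 90% power at N = 94 (HR 2.21 without censoring) | 47–79% | 93–98% regions; 92–96% region × age; 91–95% age × FT × TBSA |
| Calibrated so that the 256-cell test has 90% power at N = 94 | 98–100% | 100% |

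The 47–79% also covers two other calibrations: HR 3.26 with event shares 0.59/0.70, and 48% of NexoBrid patients done within 2 days. In the last row, three of six split sets with censoring could not reach 90% at N = 94 for any log HR up to 5 and were left out.

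6. **How often the fallback is used.** Two independent 10% checks give 1 − 0.9² = 19%. Simulation gives 19–26% under proportional hazards, 27–34% if the covariates are prognostic, and 61–86% with early benefit. Power of the whole procedure (Cox unless triggered) at log HR 1.25, proportional hazards and no censoring is 95–99% against 100% with regions; a rough check is 1 − 0.26 × (1 − 0.82) = 95%. At the unstratified-N = 94 effect it is 88–93% against 97–99% under proportional hazards, and 66–80% against 91–95% with early benefit.

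7. **Type I error.** The p-value comes from re-randomization (11.1.2), which repeats the same stratified test on each re-allocation, so sparse strata do not inflate it.

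**The case against.** **The size rests on assumptions.** This stands. Every split except age is assumed. The upper end needs TBSA above 15% in 30% of patients, which looks high because the Protocol excludes a continuous burn above 15% TBSA.

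**The effect may be large.** At the SAP's own target the whole procedure stays above 90%. With 90% early completers, fallback power is 97–100% even with 256 cells. The excision rates of 0.04 and 0.72 in MW2010-03-02 concern another endpoint, but they make a large effect plausible. Imposing event shares of 0.59/0.70 lowers fallback power at log HR 1.25 to 55–83% (against 95–99%), but the censoring mechanism is assumed and I do not rely on it.

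**A reader might infer that 13.3 shows a power of 47–79%.** It does not. Those figures need N = 94 to have come from an unstratified test, which 13.3 does not say. The only Gehan test specified for this endpoint's main analysis is the stratified one; if that was simulated, the loss is already counted. The text leaves both readings open.

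**A reader might also infer 64 × m strata**, because 11.1.3 sends centergroup to the individual centers of 11.1.11. The documents do not support this. Section 11.1.8 puts a grouped center into these analyses, and the code in 11.1.5.1 uses region indicators. It is a cross-reference slip.

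**A late change has a price.** The SAP reports that "until March 2020, 145 patients were enrolled into the study"; the trial is open label, the endpoint is measured in days, and this SAP is dated 31 May 2021. Leaving the line alone costs only the sponsor. This is a fair argument for documenting the change strictly, but not for keeping a test that may ignore a large share of the patients.

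**Conclusion.** The point holds as an avoidable and undocumented power risk in one branch of the primary analysis. It is worth fixing, with medium confidence in its size. What is certain is the 256 possible cells, the zero contribution of one-arm strata, the missing rule for them, the wrong cross-reference and the unstated strata behind N = 94. The share of patients lost (about 30–65%, outer range 17–73%) depends on splits that the documents do not give. The power cost ranges from negligible to severe, depending on the true effect and on how N = 94 was simulated. The documents do not support saying that type I error is inflated, that the primary test will fail, or that 145 patients are too few.

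**What to change.** Before the first-stage database lock, made and documented without sight of outcomes by arm:

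- Replace the five-way STRATA list with a coarse one of at most about 16 cells. Centergroup alone (the four regions of 11.1.8), region × age, or the minimization factors age × FT × TBSA would each serve.
- Drop number of TWs, which is not a minimization factor. Dropping it alone leaves 64 cells, with fallback power of 99–100% at log HR 1.25 but only 78–87% at HR 2.21.
- Correct the reference for centergroup from 11.1.11 to 11.1.8.
- State in 13.3 which strata the N = 94 simulation used, and rerun it with the specified test if they differ.
- Mirror the change in the EU SAP, since 2.5 says that both contain the same analyses.

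The cost is one line of code, one cross-reference, one sentence and possibly one rerun. There are two downsides. The fallback would adjust for fewer factors than the Cox model; with assumed prognostic effects of FT, TBSA, number of TWs and region, region-only strata still gave 94–100% power against 48–99% with 256 cells. It is also a late change to a primary-test specification in an open-label trial, credible only with the documentation above.

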11.1.4. Secondary Efficacy Analyses

The secondary endpoints will be analyzed as described below. Missing data will be handled by the methods described in Section 10.1. All secondary endpoints will be analyzed using the FAS. Sensitivity analyses will include analyzing the endpoints using the PP as analysis population.

11.1.4.1. Incidence of Surgical Excision

This is a binary yes/no variable and the proportion of patients who need excision will be compared using logistic regression. Missing data for the main analysis and for the two sensitivity analyses will be handled by the methods described in Section 10.1.3.1. The explanatory variables in the model will include treatment, center, age, %TBSA, proportion of the FT area of a patient and number of TWs (1,2,3-4, ≥5). The odds ratio of requiring surgery for NexoBrid versus SoC will be estimated from the model, as well as a 95% confidence interval and the level of statistical significance.

As sensitivity analysis, the procedure outlined above will be repeated using the PP instead of the FAS as analysis population.

A supportive analysis will be performed adjusting for other baseline variables that are imbalanced, based on the analyses described in Section 11.1.1.

As an additional analysis, the incidence of surgical excision will be compared on a wound level using a mixed logistic regression model with a random effect for patient.

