11.1.2. Re-Randomization Test

Treatment allocation will be performed in this trial by minimization, therefore the p-values reported in this trial for the main analyses of the primary and secondary endpoints, performed on the FAS, will be based on the re-randomization test. To note, all other analyses (sensitivity, supportive, additional), including analyses on PP population, will be performed without the rerandomization test.

The re-randomization test is advocated by Proschan et al (Biometrics 2011; 67:1135-41) for trials that employ minimization, and belongs to the class of tests that are based on permuting the treatment allocations of the patients.

The test works as follows. Suppose the analysis for an endpoint is performed as described in Sections 11.1.3 or 11.1.4 below and a p-value for the estimated treatment difference is p*. We now return to the list of patients in the same order as they entered the trial and re-apply the minimization procedure to their treatment allocation, as described in Appendix 13.1. Because

the procedure involves random allocations at various junctures during the trial, the next time we apply the procedure it will in general yield a different set of treatment allocations for the patients. Having obtained these new treatment allocations, we then re-analyze the data as if these had been the true treatment allocations, and obtain a new p-value p_1 and corresponding test statistic s_1 for the test of the treatment difference. We repeat this step a large number of times (in this trial we will use 8000 repeats) and obtain a set of 8000 pairs of p-values and test statistics (p_1 , s_1), (p_2 , s_2), ..., (p_{8000} , s_{8000}). If exactly n of these 8000 p-values are less than or equal to the value p^* (obtained on the real data) with the test statistic in the direction of advantage to NexoBrid, then the re-randomization test p-value is assigned the value 2*n/8000.

The random seed for the re-randomization will be 48920.

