Estimate based on study MW2004-11-02

Estimated difference in mean percent wound excised from study MW2004-11-02 (NexoBrid vs. SoC) = 15.1 - 59.6 = -44.5.

Standard error = 5.3

Target difference $\Delta = -44.5 + 5.3/2 = -41.85$.

The formula for the number of patients per group n is: $n = \frac{2(z_{\alpha} + z_{\beta})^2 \, \sigma^2}{\Delta^2}$

where

 $z_{\alpha} = 1.96$;

 z_{β} = 1.28 for a power of 90%;

 σ = the estimated common standard deviation of percent area of wound excised = 34.

For 90% power, number per group = 14

Estimate based on study MW2010-03-02

Estimated mean % area surgically excised from study MW2010-03-02: NexoBrid 3.66; SoC 58.74

Standard errors: NexoBrid 2.09; SoC 5.78

Difference: -55.08; Standard error of difference = 5.89

Target difference Δ = -55.08 + 5.89/2 ≈ -52.13.

Using a two-sided two-sample t-test with a two-sided significance level of 5%, the total sample size required to achieve a power of 90% is 24 (12 per group).

Incidence of Surgical Excision

Estimate based on study MW2004-11-02

Estimated proportions having surgical excision from study MW2004-11-02: NexoBrid 0.42; SoC 0.80

Standard errors: NexoBrid 0.057; SoC 0.044

Difference = 0.38; Standard error of difference = 0.073

Anticipated difference: 0.38-0.073/2 ≈ 0.34

We therefore take the anticipated proportion with surgical excision to be: NexoBrid 0.44 and SoC 0.78.

Using Fisher's exact test with a two-sided significance level of 5%, the total sample size required to achieve a power of 90% is 96 (48 per group).

Estimate based on study MW2010-03-02

Estimated proportions having surgical excision from study MW2010-03-02: NexoBrid 0.04; SoC 0.72

Standard errors: NexoBrid 0.023; SOC 0.052

Difference = 0.68: Standard error of difference = 0.057

Anticipated difference: $0.68-0.057/2 \approx 0.652$

We therefore take the anticipated proportion with surgical excision to be: NexoBrid 0.05 and SOC 0.70.

Using Fisher's exact test with a two-sided significance level of 5%, the total sample size required to achieve a power of 90% is 26 (13 per group).

Incidence of Autograft in DPT Wounds (wound level analysis)

Estimate based on study MW2004-11-02

Only subjects with at least one DPT target wound will be eligible for this analysis. The expected proportion of subjects with at least one DPT target wound estimated from study MW2004-11-

02 is 62.6%.

Estimated log OR using GEE approach from study MW2004-11-02 (NexoBrid vs SoC): -0.676

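### Surgical excision, second in the test hierarchy, is analysed by a 10-slope ordinary logistic regression with no named test statistic and no rule for separation; the odds ratio leans towards NexoBrid, and zero NexoBrid excisions could make the test fail

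*SAP*

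**What the plan says.** - **Model (SAP 11.1.4.1).** "This is a binary yes/no variable and the proportion of patients who need excision will be compared using logistic regression". The covariates are treatment, center, age, %TBSA, FT proportion and number of TWs in four classes. The section asks for an odds ratio, a 95% confidence interval and a significance level. It does not say whether that level comes from a Wald or a likelihood-ratio test, or what happens if the fit does not converge to finite values.
- **Center (SAP 11.1.8).** Grouped into four regions.
- **Planning rates.** SAP 9.1.2 uses 0.44 versus 0.78, from MW2004-11-02. SAP 13.3 repeats these and adds rates from MW2010-03-02: "We therefore take the anticipated proportion with surgical excision to be: NexoBrid 0.05 and SOC 0.70". The rates observed in that study were 0.04 and 0.72. SAP 13.3 does not say which scenario is the expected one.
- **Confirmatory p-value (SAP 11.1.2).** The main analysis takes its p-value from a re-randomization test. The yardstick is the model's own result ("a p-value for the estimated treatment difference is p", written `p*` there). The test counts re-allocations whose model p-value is no larger than `p*` and which favour NexoBrid, then doubles the count and divides by 8000.
- **Position (SAP 11.1.9).** "The primary and secondary endpoints of efficacy will be tested in a hierarchy", and the entry after the primary endpoint reads "2. Secondary: Incidence of surgical excision". Blood loss and the two autograft endpoints follow.
- **Missing values (SAP 10.1.3.1).** The main analysis counts them as excised.

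**The concern.** Maximum-likelihood logistic regression pushes odds ratios away from 1 when there are few events for each coefficient, so the reported effect would be too favourable to NexoBrid. A separate problem arises if one arm has no events at all. The treatment coefficient then runs off to minus infinity, its standard error explodes faster, and a Wald p-value approaches 1.

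Re-randomization does not automatically repair this, because it ranks the same model p-values. The best possible result for NexoBrid could then be reported as non-significant, and the three later endpoints could not be tested. In the scenario where this can happen, SAP 13.3 puts the enrolment needed for 90% power on blood loss at 80 patients, so a test with a good chance of success would be lost.

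**Working it through.** **1. The plan's own figures.** Exact enumeration of Fisher's test with 80 per arm, 0.44 versus 0.78, gives 99.2% power (SAP 9.1.2: 99.1%). For 90% power it gives 47 per group (SAP 13.3: 48), and 12 per group at 0.05 versus 0.70 (SAP 13.3: 13). The planning figures are essentially reproduced, but they concern Fisher's test and not the regression that will be run.

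**2. Slopes.** Treatment 1 + region 3 + age 1 + %TBSA 1 + FT proportion 1 + number of TWs 3 = 10.

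**3. Expected events** (145 children at 1:1, taken as 72 NexoBrid and 73 SoC).
- 0.05 versus 0.70: 72 × 0.05 = 3.6 and 73 × 0.70 = 51.1. The total is 54.7, or 5.5 per slope.
- 0.44 versus 0.78: 72 × 0.44 = 31.7 and 73 × 0.78 = 56.9. The total is 88.6 events and 56.4 non-events; the rarer outcome gives 5.6 per slope.

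**4. Chance of no NexoBrid event.** 0.95^72 = 0.025; 0.96^72 = 0.053; 0.56^72 is about 7 × 10⁻¹⁹.

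**5. Bias of the odds ratio.** True values: (0.05/0.95)/(0.70/0.30) = 0.0226 and (0.44/0.56)/(0.78/0.22) = 0.222. Trials of 145 children were simulated with the SAP's minimization (switch to the random element assumed after patient 50), assumed covariate distributions and no covariate effects. With no covariate effects, adjusted and unadjusted odds ratios coincide, so the gap below is estimation bias.

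| Scenario | True OR | Median ML OR | Median Firth OR |
|---|---|---|---|
| 0.05 vs 0.70 (1000 trials) | 0.0226 | 0.0144 | 0.0245 |
| 0.44 vs 0.78 (500 trials) | 0.222 | 0.191 | 0.217 |

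The ML median is too extreme by 1 − 0.0144/0.0226 = 36% and 1 − 0.191/0.222 = 14%. Adding covariate effects in the first scenario gave 0.0134 (ML) and 0.0234 (Firth). In a separate set of 1500 trials at 0.44 versus 0.78, the nominal 95% interval covered the truth 93.0% of the time with ML and 95.2% with Firth.

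**6. Zero NexoBrid events.** Three simulated data sets with 50 or 51 SoC events and no NexoBrid events, each with 1000 re-allocations by minimization:

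| Model p-value used | `p*` | Re-randomization p |
|---|---|---|
| Wald | 0.9994 to 0.9996 | 0.994 to 1.022 |
| Likelihood ratio | about 10⁻²³ to 10⁻²⁴ | 0 |

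With `p*` near 1, practically every re-allocation that points towards NexoBrid counts. That is about half of them, and doubling brings the result to about 1 (the rule has no cap, hence 1.022). When the fitting iterations were capped early, the Wald `p*` was 0.89 and the re-randomization p 0.88, which is still non-significant.

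**7. One or more NexoBrid events.** With one event the median Wald p was about 7 × 10⁻⁷, and in the data set tried the re-randomization p was 0. Of the 1000 sparse-scenario trials, 28 had no NexoBrid event. Of the other 972, 0.6% (6 trials) failed, which was attributed to separation through another covariate. So 34 failed, and power at the model level was 96.6% with Wald against 100% with the likelihood ratio.

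**The case against.** A reader might infer that the SAP expects only about four NexoBrid excisions and that a zero count would necessarily give p near 1. The documents do not support that.

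- **Event count.** The 0.05 rate is one of two scenarios and comes from a study SAP 13.3 describes as adult. The 0.44 rate comes from a study that included children (SAP 9.1), gives about 32 events, and makes a zero count practically impossible.
- **Test statistic.** SAP 11.1.4.1 does not name a Wald test. SAP 11.1.3 does specify coefficient over standard error for the primary Cox model, which makes Wald a plausible default but does not settle it. With a likelihood-ratio p the same data give an overwhelming result.
- **Missing data.** One NexoBrid child with a missing value is counted as excised in the main analysis, which removes the separation in the treatment arm. SAP 10.1.3.1 expects little or no missing data, so this cannot be relied on, and neither missing-data sensitivity analysis has this protection.
- **Size.** Even in the sparse scenario, Wald power is 96.6%. The biased odds ratio does not drive the confirmatory decision, which rests on the re-randomization p.

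All four points stand and limit the claim. Two things remain. The odds ratio and interval are required outputs and lean towards NexoBrid in both scenarios. And the current text allows two opposite conclusions from the same zero-event data. Naming a likelihood-ratio test would cure the p-value alone; it would leave the bias, and would leave no finite log odds ratio to report when there are no NexoBrid events.

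**Conclusion.** The point holds in a conditional form and is worth correcting.

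- **Estimation, both scenarios.** The ML odds ratio is too favourable to NexoBrid: about 0.014 against 0.023, and about 0.19 against 0.22 with roughly 93% coverage. The second bias is modest.
- **Testing, sparse scenario only.** There is a 2.5% (rate 0.05) to 5.3% (rate 0.04) chance of no NexoBrid excision, lower if any NexoBrid value is missing. The hierarchy would then stop if, and only if, the model p-value is a Wald p or one that behaves like it.

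The slope count and the zero-event probabilities follow from the SAP's figures, taking 72 children in the NexoBrid arm. The bias and coverage figures depend on assumed covariate distributions, and the simulated allocation on an assumed date for the change in minimization.

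**What to change.** In SAP 11.1.4.1:

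1. Fit the same covariates by Firth penalised likelihood (the FIRTH option in PROC LOGISTIC).
2. Report the odds ratio with a profile-penalised-likelihood 95% confidence interval.
3. State that the penalised likelihood-ratio p-value, not a Wald p-value, serves as `p*` and as each re-allocation's p-value in the test of SAP 11.1.2.
4. Use the same model for the PP analysis and the two missing-data sensitivity analyses.

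The covariates, analysis set and hierarchy do not change. The cost is a short addition to the SAP, one model option, and code to extract the penalised likelihood-ratio p-value from the observed fit and the 8000 refits. The odds ratio will come out slightly less favourable to NexoBrid.
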